8.6 Follow-Up of Adverse Events

Investigators must follow up participants with SAEs until the event has stabilized or resolved whichever is the latter. In the case of non-serious AEs, follow-up should occur until the participant completes the study. Records of the participant's progress should be maintained until the conclusion of the study and thereafter in a participant's medical history at the relevant investigational site. Details of the participant's progress must be submitted to the Starpharma and Study Monitor on request.

8.7 Regulatory Reporting Requirements

Starpharma have a legal responsibility to notify the local regulatory authority (ies), and other overseas agencies (if applicable) about the safety of the product/drug under clinical investigation.

Prompt notification of SAEs by the Investigator is essential so that legal obligations and ethical responsibilities towards the safety of other participants are met.

8.8 IEC/IRB Reporting Requirements

The time frame within which the Investigators must be notified of deaths, study drug related and/or unexpected SAEs is stipulated by the local regulatory authorities.

It is the Investigators' responsibility to comply with the requirements for IEC/IRB notification. Each Investigator will notify the IEC/IRB, by promptly forwarding the Safety Report completed by Starpharma or its agent, for all onward reportable SAEs.

8.9 Pregnancy

Participants who become pregnant during the study period (up to and including 30 days after the last use of investigational product) must not use any further investigational product, and are to be instructed that they immediately notify the Investigator.

Starpharma must be notified within 24 hours of the Investigator learning of the pregnancy. The Investigator will be asked to complete the SAE CRF without the 'criteria of seriousness' checked.

Participants will be withdrawn from the clinical study and the procedure for discontinuation of participants who becomes pregnant will be followed (see Section 7.1.7).

Whenever possible, a pregnancy in participants exposed to study product should be followed to term. Any premature terminations and the status of the mother and child after delivery should be reported to Starpharma. The Pregnancy Outcome and Questionnaire Form may be used by the Investigator to record details of the pregnancy outcome. The form includes provision to record the mothers' status during the pregnancy, relevant medical history, and details of the health of the baby(ies) on delivery.

If a congenital anomaly/birth defect occurs this must be reported as an SAE.

8.10 Safety Monitoring

The following AEs will be reported by the Investigator to the study team on an ongoing basis:

- Any signs and symptoms of genital irritation graded at Grade 2 or above
- Any other AEs considered to be potentially related to study product reported at Grade 3 or above
- All SAEs

If the Investigator and/or study team consider that an abnormally high number of signs and symptoms of genital irritation, other Grade 3 AEs, or SAEs are being reported that have a potential causality to study product, then a blinded review of the AE data will be conducted. This

blinded review will include the Investigator, Medical Expert and Starpharma. From this review, one or more of the following recommendations may be made:

- No action need be taken;
- A protocol amendment may be implemented;
- Additional external advice may be sought;
- An independent review of the unblinded data may be conducted;
- The study may be paused or halted;
- Other appropriate recommendations may be made.

Actions will be reported to the IRB and/or relevant regulatory authorities if necessary according to their requirements.

9. CLINICAL MANAGEMENT

9.1 Participant Completion

A participant will be deemed to have completed the study once all trial procedures have been conducted. Study participants who have a relapse of their BV during the follow-up phase of the study will still be considered completed participants, and will be offered rescue therapy as per local practice, after completing the Follow-Up Visit. Any AEs or SAEs still ongoing will be followed in accordance with Section 8.

9.2 Treatment Non-Responders

A participant will be considered to be a "Treatment Non-Responder" if she reports that the abnormal discharge associated with BV has not improved at Visit 3 and wishes to receive alternative therapy. These participants will not be required to attend the TOC Visit, and will be provided with rescue therapy as per local practice. These women will receive a telephone call at the time that the TOC visit would have been scheduled to assess response to rescue therapy and any adverse effects of the therapy (*e.g.* candidiasis).

9.3 Study Participant Withdrawal

The investigator should make every reasonable effort to keep each participant in the study, except where termination or withdrawal is for safety reasons. However, if the investigator removes a participant from the study, or a participant declines further study participation, a complete exit evaluation must be performed in the form of the Withdrawal Visit. Study participants who do not respond to treatment are not considered withdrawals, but "Treatment Non-Responders" and are handled as above. Should a participant decide to withdraw from the study, all efforts will be made to complete and report the reason(s) for withdrawal and observations as thoroughly as possible.

The investigator may cease study product and withdraw the participant, or the participant may withdraw herself from participation in the study at any time and for any reason. The following are considered justifiable reasons for subject withdrawal from the study:

- The need to take medication which may interfere with study measurements;
- Intolerable/unacceptable adverse experiences;
- Major violation or deviation of study protocol (see Section 12.9);
- Participant unwilling to proceed and/or consent is withdrawn;
- Participant is pregnant;
- Withdrawal from the study is, in the investigator's judgment, in the best interest of the participant;
- Participant unblinded to treatment assignment;
- Lost to Follow-up;
- Other (e.g. personal reasons).

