6.8 Rescue Medication

As it may take a couple of weeks for BV to fully resolve and the vaginal environment to return to normal, every effort should be made to retain study participants in the trial up to the final visit (Visit 4, TOC). However if participants are not satisfied that symptoms are improving, rescue medication/therapy may be provided if:

- at Visit 3, the study participant reports no improvement in BV-associated discharge and wishes to receive alternative therapy;
- after Visit 3 but prior to Visit 4, the study participant reports that symptoms have returned and wishes to receive alternative therapy.
- at Visit 4 the investigator determines that the BV has recurred, or study participant reports that symptoms have returned.

Prior to administration of rescue therapy, participants are to be assessed as per their next scheduled study visit (*i.e.* Visit 3 or Visit 4 (TOC)). Rescue medication will be the standard therapy for BV according to local practice at the study site. Details of any rescue medication provided to a study participant must be entered in to the CRF, and marked as such. Study participants who receive rescue therapy prior to Visit 4 (TOC) are considered to be "Treatment Non-Responders". Women who receive rescue therapy will continue to be assessed during the remaining study visits.

Medication may also be provided by the study participant's primary care physician after the participant has completed the study if her BV recurs after Visit 4. No details of any therapy received after completion of the study is to be provided.

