7.1.6 Withdrawal Visit

Any participant who prematurely withdraws from the study, for whatever reason, will be asked to attend a Withdrawal Visit as soon as possible and ideally within 2 weeks of finishing study treatment administration. This includes women who enroll in to the study with a positive local test for BV but without a confirmed Nugent score of 4 or more, where the Nugent score is subsequently determined to be less than 4, and are required to withdraw. Women who require rescue therapy are not considered withdrawals unless they do not complete the TOC visit; they are classified as "Treatment Non-Responders". Follow-up procedures for female participants who become pregnant during the study are outlined in Section 7.1.7. The Withdrawal Visit will include the following procedures:

- Review of protocol compliance
- Review diary card
- Review of AEs and concomitant medications (see Sections (see Sections 7.3.5 and 8).
 Participant will be referred to her primary care physician for any ongoing AEs as appropriate. Any ongoing SAEs should be followed until resolution or considered as stable
- Pelvic examination including vaginal swab for Gram stain, semi-quantitative analysis (subset only) and storage sample (see Sections 7.2.3 and 7.2.6))
- Assessment of BV according to the Amsel's Criteria

- Pregnancy testing (see Section 7.2.6)
- Completion of Symptom Questionnaire (see Section 7.2.7)
- Completion of Acceptability Questionnaire [TSQM] (see Section 7.2.8)

Women in whom the BV has been found to recur at this Withdrawal Visit will receive rescue medication for their BV according to local practice as outlined in Section 6.8. Any rescue therapy will be documented in the participant's CRF.

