7.3.5 Concomitant Medication

There will be no restriction on concomitant medications administered during the study, with the exception of those outlined below:

To protect the integrity of the lower genital tract and reduce the possibility of AEs due to agents other than the study products, any spermicides, diaphragms, or contraceptive vaginal rings should not be used during this study.

Similarly, study participants requiring vaginal preparations for conditions other than their BV, such as anti-fungals, or study participants requiring antibiotics (by any route), may not be enrolled in to the study until at least 14 days after the last dose, and resolution of symptoms. Antibiotics by any route may not be administered during the on-study period, and if required will lead to cessation of study product, however participants should continue to undergo the remaining study visits. Symptoms of candidiasis occurring in study participants during the study should be treated with oral preparations where possible, if vaginally applied preparations are required, the participant will be required to withdraw from the study. All medication is to be recorded in the CRF. Participants will be required to withdraw from the study if they require treatment for an STI.

Participants will be discouraged from using additional vaginal lubricants; however, if these are used during the study, the participant will not be required to withdraw and their use is to be recorded in the concomitant medication section of the CRF.

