8.2 Reporting of an Adverse Event

8.2.1 Timeframe for Reporting Adverse Events

AE reporting will begin from first dose and will continue throughout the study until the TOC visit. AEs occurring during the screening phase of the study and before administration of study product are to be reported in the Screening Signs and Symptoms section of the CRF. AEs occurring thereafter (*i.e.* after first administration of study product) are to be reported in the AE reporting pages of the CRF.

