10.8 Statistical and Analysis Plan

A final statistical analysis plan will be developed and approved by Starpharma prior to database lock. Statistical analyses will be performed after all participants have ended their participation in the study. Participants withdrawn prior to randomization will not be assessed for outcome variables or safety parameters. The following is a summary of the planned analyses; full details are captured in the statistical analysis plan. Any deviations to be made from this summary plan and planned analyses will be documented in the statistical analysis plan.

All hypotheses will be tested for statistical significance with two-tailed p-values unless otherwise noted. Results of all tests will be considered statistically significant if their p-value is less than or equal to 0.048 as per the O'Brien-Fleming α adjustment for the planned interim analysis.

Continuous variables will be summarized using descriptive statistics (N, mean, standard deviation, median, minimum and maximum), while categorical variables will be summarized as counts and percentages of participants in each category. Results will be presented by treatment group as appropriate.

Efficacy analyses will be presented using the MITT and per-protocol populations. For efficacy analyses, all missing values due to participant withdrawal and missed visits as well as values outside of analysis windows will be imputed using the last observation carried forward (LOCF) method as appropriate. For sensitivity analysis, efficacy results will also be presented with "as observed" results.

All baseline and demographic summaries will be based on the MITT dataset. No statistical comparisons between treatment groups will be made on demographic and baseline characteristics.

If there is a discrepancy between the locally and centrally read Nugent score, the locally read score will take precedence over the centrally read score in determining whether a participant is eligible to enter the study. The centrally read score will take precedence over the local score in determining study endpoints.

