12.9 Protocol Deviations

Deviations from the protocol should not be made other than as part of a protocol amendment agreed with Starpharma, except where necessary to eliminate an immediate hazard to study participants or when the change(s) involves only logistical or administrative aspects of the study.

All protocol deviations must be noted and explained in the Investigator's file. Participants may only be withdrawn from the study or statistical analyses during a blinded review of the data.

Protocol deviations can be divided into two categories as follows:

Minor Protocol Deviations

 all instances where the protocol specified instructions have not been followed during the on-study period.

For example:

- a visit occurs outside the acceptable window period;
- the required number of applications of study product have not been reached;
- concomitant vaginal products are used.

Major Protocol Deviations (also known as "Protocol Violations")

- when the participant did not meet all inclusion and/or exclusion criteria prior to entry into the study;
- if additional procedures are performed that are not specified in the protocol.

All major protocol deviations are to be reported to Starpharma, and the IRB if required.

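### Section 9.3 allows a randomised woman to be withdrawn for a major deviation or for being unblinded, against Section 12.9, and her Day 21-30 primary outcome can be lost as a result

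*Protocol*

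**What the plan says.** Protocol Section 9.3 asks the investigator to make reasonable efforts to retain each woman. It then permits the investigator to stop gel and withdraw her, and lists justifiable reasons. Two of them are "Major violation or deviation of study protocol (see Section 12.9" and "Participant unblinded to treatment assignment".

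Section 12.9 defines major deviations as failed eligibility criteria or procedures outside the protocol. It also states: "Participants may only be withdrawn from the study or statistical analyses during a blinded review of the data". Section 10.3 places decisions on evaluability in a blinded review before database lock.

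A withdrawn woman has a Withdrawal Visit (7.1.6) with the Test of Cure (TOC) procedures, including an Amsel assessment, as soon as possible and "ideally within 2 weeks of finishing study treatment administration". The primary endpoint is Clinical Cure at TOC, Day 21-30. Under Section 10.8, "all missing values due to participant withdrawal and missed visits as well as values outside of analysis windows will be imputed" by last observation carried forward (LOCF). Section 10.9 analyses the primary variable in MITT (as observed), MITT (LOCF) and Per-Protocol.

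On retention, Section 6.8 notes that BV may need a couple of weeks to resolve and says "every effort should be made to retain study participants in the trial up to the final visit (Visit 4, TOC".

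**The concern.** There are two problems. First, Section 9.3 sends the reader to Section 12.9 for a withdrawal reason, and Section 12.9 forbids withdrawing anyone outside a blinded data review. An investigator who has just found an eligibility violation gets opposite instructions.

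Second, ending follow-up for these events can discard the primary outcome of women who still belong in the main efficacy set. A deviation or an unblinding affects how a woman's data should be classified. It is not in itself a reason to stop observing her. If she leaves early, her Clinical Cure status at Day 21-30 may never be measured, and no analysis plan can recover a visit that was not held.

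There is a smaller safety cost. Section 8.2.1 says "AE reporting will begin from first dose and will continue throughout the study until the TOC visit", so new non-serious events arising after exit are not captured. AEs already present are still followed (8.3), and SAEs are reported to 30 days after the last dose (8.2.2).

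**Working it through.** **The two rules side by side**

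| | Section 9.3 | Section 12.9 |
|---|---|---|
| Who acts | Investigator | Blinded data review |
| When | During the study | At the review only |
| Major deviation | Justifiable reason to withdraw | No withdrawal outside the review |
| Participant unblinded | Justifiable reason to withdraw | No withdrawal outside the review |

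Section 12.9 cannot simply prevail. Read literally, it would also bar withdrawals required elsewhere: screening Nugent score below 4 (5.1.3, 7.1.1, 7.1.6, 7.2.6.3), treatment for an STI (7.2.6.1, 7.3.5) and pregnancy (8.9). Both sections need rewording.

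**Is withdrawal needed?**
- The Per-Protocol set (10.2.6.5) excludes women with eligibility violations and women who were unblinded.
- The other kind of major deviation, an unplanned extra procedure, can be judged at the blinded review (10.3). The Per-Protocol list is stated not to be exhaustive.
- MITT (10.2.6.3) requires randomisation, at least one dose, a post-baseline efficacy assessment, and no antibiotics (other than rescue) or vaginal antifungals. It does not require freedom from deviations or unblinding.

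So these women can belong in MITT, and the supportive set is already built to deal with them.

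**Timing of the exit reading**
- Inputs: dosing on Days 1 to 7; Withdrawal Visit ideally within 14 days of the last dose; TOC window Day 21-30.
- Latest ideal exit day = day of last dose + 14, which runs from 1 + 14 = Day 15 to 7 + 14 = Day 21. Only a woman who dosed to Day 7 can reach even the first day of the window within the ideal timing.
- A woman withdrawn and assessed at Visit 3 (Day 9-12) is read between 21 − 12 = 9 and 30 − 9 = 21 days before TOC.

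An out-of-window exit reading gives an earlier value carried forward in MITT (LOCF) and no TOC value in MITT (as observed). Section 6.8's own remark on time to resolution is why the two readings cannot be treated as equivalent.

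**Weight of one woman**

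1/33 = 3.0% and 1/28 = 3.6% of an arm's cure rate.

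**The plan's sample size (10.4)**

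Inputs: 50% vs 15%, two-sided alpha 0.048, 80% power. With pooled variance and no continuity correction, n = 28 per arm; 28/0.85 = 32.9, so 33 randomised. This reproduces the protocol. Power is 87.3% at 33 per arm and 81.1% at 28. Since 33 × 0.85 = 28.05, five losses per arm are already allowed for, and Section 9.5 permits replacement if withdrawals exceed 15%. No loss of planned power is claimed.

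**Direction of error (illustration on assumed figures)**

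Let a fraction w of each arm carry an earlier reading, with early cure of 30-70% on active and 15-30% on placebo:

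expected difference = [(1 − w) × 0.50 + w × early active] − [(1 − w) × 0.15 + w × early placebo]

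- w = 5%: lowest (30%, 30%) 0.490 − 0.1575 = 33.25 points; highest (70%, 15%) 0.510 − 0.150 = 36.0 points.
- w = 15%: lowest 0.470 − 0.1725 = 29.75 points; highest 0.530 − 0.150 = 38.0 points.

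Against the planned 35 points, the error can go either way. The documents give no value for w or for the early cure rates. A w of 15% from these two reasons alone would equal the whole planned drop-out allowance, so it is an outer bound.

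**The case against.** The strongest reply is that little of this will happen. Section 9.3 is permissive and opens with an effort to retain. Major deviations are narrowly defined: missed doses, late visits and concomitant vaginal products count as minor. The eligibility failure the protocol foresees after randomisation, a screening Nugent score below 4, has its own mandatory withdrawal. Unblinding is not expected at all and needs a Safety Monitor ruling (6.5). This stands: the number affected is probably small.

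It can also be said that Section 12.9 was meant only for exclusion from analysis, so that a small deletion there would remove the contradiction. That is a fair reading of intent, and it is half of the fix. It would still leave Section 9.3 naming these two events as justified exits, which weakens its own retention sentence.

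Third, LOCF applies as appropriate, the analysis windows are not defined in the protocol, and how an exit visit maps to TOC is ordinary SAP material. True, and the timing is only an ideal. But mapping rules cannot supply a Day 21-30 reading that was not taken. The LOCF problem is shared by every withdrawal; these withdrawals differ in being avoidable.

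Finally, after a code-break the investigator knows the allocation and normally performs all the pelvic examinations (7.2.3), so a retained woman may bring an unblinded discharge assessment into MITT. That is a real trade-off. However, the same investigator would ordinarily make the exit Amsel assessment too, so withdrawal does not avoid the bias.

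**Conclusion.** The concern holds. Sections 9.3 and 12.9 contradict each other on withdrawal for a major deviation or participant unblinding. Following Section 9.3 can replace or lose the primary outcome of a woman who can still qualify for MITT, for events the Per-Protocol set and the blinded review already cover.

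The effect is probably small. How many women would be affected and the direction of error are unknown, planned power is not at issue, and each woman is worth 3.0 to 3.6 percentage points in her arm. The conclusion assumes that sites would use the permission in Section 9.3 and that exit visits follow the ideal timing. It is worth correcting because the conflict is plain and the correction is cheap.

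**What to change.** **Section 9.3.** Remove the major-deviation and participant-unblinding items from the reasons for study withdrawal, or make them reasons to stop gel only. Add that neither is by itself a reason for the investigator to end follow-up, so that the open-ended withdrawal clause does not bring them back. State that such women:
- are asked to attend Visit 3 and TOC;
- stay in the Safety set if dosed, and in MITT if they otherwise meet its definition;
- are considered for exclusion only from the Per-Protocol set, at the blinded review under Section 10.3.

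Expressly keep the mandatory withdrawals for screening Nugent score below 4, STI treatment and pregnancy. Leave the vaginal antifungal rules unchanged.

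**Section 12.9.** Reword the blinded-review sentence to cover exclusion from statistical analysis only.

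**Cost.** Wording in two sections and a few visits already scheduled. The protocol has the model in Section 7.3.5, where a need for antibiotics, "if required will lead to cessation of study product, however participants should continue to undergo the remaining study visits". The downside is that MITT keeps some outcomes from women with deviations or unblinding; the supportive Per-Protocol analysis leaves out the eligibility violators and the unblinded women.
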